6.2 Safety Assessments

6.2.1 Vital Signs and Physical Measurements (Height and Weight)

Body weight and height will be recorded at the scheduled visits as outlined in [Table 1](#).

6.2.2 Electrocardiogram (ECG)

A standard 12-lead ECG will be recorded during the Screening Phase and at the scheduled visits as outlined in [Table 1](#). A central ECG service will be utilized for all ECGs and the investigator will determine if any abnormalities are clinically significant or not.

6.2.3 Physical Exam

Subjects will undergo a routine physical examination during the Screening Phase and at the scheduled visits as outlined in [Table 1](#).

6.2.4 Laboratory Assessments

6.2.4.1 Safety Laboratory Testing

Blood and urine samples will be obtained as outlined in [Table 1](#) for clinical laboratory evaluations. A central laboratory vendor will be utilized for this study and a laboratory manual will be provided to each site. **If possible, subjects should be fasting for a minimum of 8 hours prior to all blood draws.** However, if a subject is not fasting at a given visit, the blood draw should still be performed, and the non-fasting status should be documented.

Hematology: Hemoglobin, hematocrit, red blood cell count, white blood cell count (WBC) with differential, and platelets.

Blood chemistry/electrolyte: Sodium, potassium, chloride, bicarbonate, calcium; glucose, BUN (urea), serum creatinine, uric acid, ALT, AST, alkaline phosphatase, LDH, total protein, albumin, total bilirubin, direct bilirubin, indirect bilirubin, CK. End of Treatment Visit – elevations in CK (>1.5xULN) may have further CK fractionation tests performed through the central lab.

Lipid panel: Cholesterol, LDL, HDL, triglycerides (Screening Only).

Estimated glomerular filtration rate: eGFR using the estimated MDRD formula will be calculated and reported by the central lab at each visit that clinical laboratory tests are collected as outlined in Table 1.

Urinalysis: pH, specific gravity, ketones, nitrites, urobilinogen, leukocyte esterase, protein, glucose and blood. If blood, protein or leukocytes are positive, reflex to microscopic examination.

Urine Drug Screen: For drugs of abuse.

6.2.4.2 *Pregnancy Testing*

Pregnancy tests will be conducted (serum, urine, or home pregnancy test), if appropriate prior to randomization, and as outlined in [Table 1](#).

6.2.5 **Sheehan Suicide Tracking Scale**

The Sheehan STS is a prospective, subjects self-reported or clinician administered rating scale that contains 16 questions to track both treatment-emergent suicidal ideation and behaviors [16, 17]. If the investigator determines that a subject is at risk of suicide or self-harm, appropriate measures to ensure the subject's safety and obtain mental health evaluation must be implemented. The subject must immediately be discontinued from the study. The event should be recorded as either an AE or SAE as determined by the investigator and reported within 24 hours to the Sponsor.

6.3 **Efficacy Assessments**

6.3.1 **Pain**

Subjects are given an eDiary to record their migraine pain score, on a 4-point numeric rating [no pain, mild pain, moderate pain, severe pain] at the time points indicated in Table 1.

6.3.2 Nausea, Phonophobia and Photophobia

The migraine associated symptoms of photophobia, phonophobia and nausea are measured on a two point scale (present or absent), using the eDiary, at the time points listed in Table 1. If a subject reports the presence of a symptom, the subject is then asked to rate the severity of the symptom on a four point scale (none, mild, moderate or severe). All assessments are done using the eDiary.

The subjects are also asked to identify their most bothersome symptom on the eDiary (nausea, phonophobia or photophobia) at the onset of the migraine to be treated. The most bothersome symptom must be identified before the subject takes study medication.

6.3.3 Rescue Medication

The subject's use of rescue medication is recorded by the subject in a paper diary.

6.3.4 Functional Disability

Impact of treatment on functional disability will be assessed using a single-question scale. Subjects rate the level of disability they perceive as a result of their migraine in performing normal actions. This is done in the eDiary, at the times indicated in Table 1, using a 4 point numeric rating scale: Normal Function, Mild Impairment, Severe Impairment, Required Bedrest.

6.3.5 Migraine Quality of Life Questionnaire

Impact of treatment on subject-reported quality of life will be assessed using The Migraine Quality of Life Questionnaire (MQoLQ). The MQoLQ is a 15-item instrument that has been validated in migraine subjects to measure the short-term impact of treatment (within 24-hours) on migraine-specific domains: work, social function, energy, vitality, feelings, concerns, and migraine symptoms. The eDiary is used to evaluate the Migraine Quality of Life Questionnaire at 24 hours post-dose (see Table 1).

6.3.6 Migraine Preference of Medicine

The Preference of Medication Scale (PoMs) is a brief scale that captures the subjects' perception of whether the medication they are taking has had a greater benefit compared with previous medications to treat their pain. The eDiary is used to evaluate the Preference of Medication Scale at 24 hours post-dose (see Table 1).

6.4 Early Discontinuation from the Study

Subjects MUST discontinue investigational product (and non-investigational product at the discretion of the investigator) for any of the following reasons:

- Withdrawal of informed consent (subject's decision to withdraw for any reason)
- Any clinical adverse event (AE), laboratory abnormality or intercurrent illness which, in the opinion of the investigator or sponsor, indicates that continued participation in the study is not in the best interest of the subject
- Pregnancy
- Termination of the study by Biohaven Pharmaceuticals
- Loss of ability to freely provide consent through imprisonment or involuntary incarceration for treatment of either a psychiatric or physical (e.g., infectious disease) illness

All subjects who discontinue should comply with protocol specified End of Treatment procedures as outlined in [Table 1](#). The only exception to this requirement is when a subject withdraws consent for all study procedures or loses the ability to consent freely (i.e., is imprisoned or involuntarily incarcerated for the treatment of either a psychiatric or physical illness).

7 STUDY DRUG MANAGEMENT

7.1 Description of Study Drug

7.1.1 Investigational Product

An investigational product, also known as investigational medicinal product in some regions, is defined as follows:

A pharmaceutical form of an active substance or placebo being tested or used as a reference in a clinical study, including products already with a marketing authorization but used or assembled (formulated or packaged) in a way different from the authorized form, or used for an unauthorized indication, or when used to gain further information about the authorized form.

The investigational product should be stored in a secure area according to local regulations. It is the responsibility of the investigator to ensure that investigational product is only dispensed to study subjects. The investigational product must be dispensed only from official study sites by authorized personnel according to local regulations.

The rimegepant ODT and the matching placebo appear identical visually, via touch, smell and taste.

7.1.2 Non-investigational Product

Other medications used as support or escape medication for preventative, diagnostic, or therapeutic reasons, as components of the standard of care for a given diagnosis, may be considered as non-investigational products.

In this protocol, non-investigational product(s) is/are: Not applicable for this study.

7.1.3 Packaging, Shipment and Storage

The product storage manager should ensure that the study drug is stored in accordance with the environmental conditions (temperature, light, and humidity) as determined by the sponsor. If concerns regarding the quality or appearance of the study drug arise, do not dispense the study drug and contact the sponsor immediately.

7.2 Dose and Administration

7.2.1 Method of Assigning Subject Identification

At the time of enrollment, immediately after written informed consent is obtained and before performing any study-related procedures, each subject will be assigned an unique sequential 4-digit subject number beginning with 0001, 0002, 0003, etc. for identification

throughout the study through an IWRS. This subject number must not be reused for any other subject in the study. The physician/coordinator must contact the IWRS to enroll each subject into a centralized database at the time of signing consent.

After completion of all screening evaluations all eligible subjects will be randomized in a 1:1 ratio to the rimegepant or placebo treatment groups. **The randomization will be stratified by the use of prophylactic migraine medications (yes or no). It is important for you to correctly enter subjects who are using prophylactic migraine medication in the IWRS system. Once a patient is stratified in the IWRS, this cannot be changed and will be considered a deviation.**

Randomization schedules will be generated and kept by the IWRS vendor in a secure network folder with access limited to only unblinded team members. Each subject who is qualified for treatment will be randomized via the IWRS randomization option. Subjects will maintain their subject number assigned at screening throughout the trial. The IWRS will provide the double-blind treatment assignments.

The randomization will trigger a bottle number for the randomized treatment type. The drug will be dispensed at the time of randomization.

7.2.2 Selection and Timing of Dose and Administration

Study medication (one 75 mg orally disintegrating tablet or matching placebo) will be packaged in a blister card. There are no dose adjustments in this study and subjects will receive one dose to treat one migraine headache of moderate or severe intensity within 45 days of randomization (Baseline Visit). Subjects will be dispensed the study medication at randomization (Baseline Visit) and will take the ODT from the kit at the time of moderate or severe migraine headache onset ***ONLY after answering questions regarding their migraine symptoms in the eDiary*** device. The tablet should be placed under the tongue until fully dissolved then swallowed. Subjects should be instructed to use dry hands when handling the study medication.

7.2.3 Dose Modifications

There will be no dose adjustments in this study.

7.3 Blinding and Unblinding

Blinding is critical to the integrity of this clinical study. However, in the event of a medical emergency or pregnancy in an individual subject, in which knowledge of the investigational product is critical to the subject's management, the blind for that subject may be broken by the treating physician.

Before breaking the blind of an individual subject's treatment, the investigator should have determined that the information is necessary, (i.e., that it will alter the subject's immediate management). In many cases, particularly when the emergency is clearly not

investigational product related, the problem may be properly managed by assuming that the subject is receiving active product without the need for unblinding.

In cases of accidental unblinding, contact the Medical Monitor and ensure every attempt to preserve the blind is made.

7.4 Treatment Compliance

Responsible study personnel will dispense the study drug. Accountability and compliance verification should be documented in the subject's study records.

Subjects have to be counseled on the importance of taking the study drug as directed when a migraine occurs and reaches moderate or severe intensity. If the subject does not have a migraine or take their study medication within 45 days of the Baseline Visit, they should return to the clinic for their End of Study Visit and return their study medication.

7.5 Destruction and Return of Study Drug

If the study drug (those supplied by the sponsor or sourced by the investigator) are to be destroyed on site, it is the investigator's responsibility to ensure that arrangements have been made for the disposal, procedures for proper disposal have been established according to the applicable regulations, guidelines and institutional procedures, and appropriate records of the disposal have been documented. The unused study drugs can only be destroyed after being inspected and reconciled by the responsible BHV Study monitor or the sponsor's designee unless this is against institutional policy.

All unused and/or partially used study drug may be destroyed on site providing the site has an applicable standard operating procedure on file.

8 ADVERSE EVENTS

An Adverse Event (AE) is defined as any new untoward medical occurrence or worsening of a pre-existing medical condition in a subject or clinical investigation subject administered an investigational (medicinal) product and that does not necessarily have a causal relationship with this treatment. An AE can therefore be any unfavorable and unintended sign (including an abnormal laboratory finding for example) symptom, or disease temporally associated with the use of the investigational product, whether or not considered related to the investigational product.

Adverse events can be spontaneously reported or elicited during an open-ended questioning, examination, or evaluation of a subject. In order to prevent reporting bias, subjects should not be questioned regarding the specific occurrence of one or more AEs.

Subjects should be instructed to notify the Investigator when a Serious Adverse Event occurs.

There are two types of adverse events, Serious Adverse Events (SAE) and Non-Serious Adverse Events (AEs).

8.1 SERIOUS ADVERSE EVENT

8.1.1 Definition of Serious Adverse Event (SAE)

A SAE is any event that meets any of the following criteria at any dose:

- Death
- Life-threatening
- Inpatient hospitalization or prolongation of existing hospitalization
- Persistent or significant disability/incapacity
- Congenital anomaly/birth defect in the offspring of a subject who received rimegepant
- Other: Important medical events that may not result in death, be life-threatening, or require hospitalization, may be considered an SAE when, based upon appropriate medical judgment, they may jeopardize the subject and may require medical or surgical intervention to prevent one of the outcomes listed in this definition. Examples of such events are (but not limited to):
 - Intensive treatment in an emergency room or at home for allergic bronchospasm
 - Blood dyscrasias or convulsions that do not result in inpatient hospitalization
 - Development of drug dependency or drug abuse
 - Potential drug-induced liver injury

Definition of Terms

Life threatening: An AE is life threatening if the subject was at immediate risk of death from the event as it occurred; i.e., it does not include a reaction that if it had occurred in a more severe form might have caused death. For example, drug induced hepatitis that resolved without evidence of hepatic failure would not be considered life threatening even though drug induced hepatitis can be fatal.

Hospitalization: AEs requiring hospitalization should be considered SAEs.

Hospitalization for elective surgery or routine clinical procedures that are not the result of AE (e.g., elective surgery for a pre-existing condition that has not worsened) need not be considered AEs or SAEs. If anything untoward is reported during the procedure, that

occurrence must be reported as an AE, either 'serious' or 'non-serious' according to the usual criteria.

In general, hospitalization signifies that the subject has been detained (usually involving at least an overnight stay) at the hospital or emergency ward for observation and/or treatment that would not have been appropriate in the physician's office or outpatient setting. When in doubt as to whether 'hospitalization' occurred or was necessary, the AE should be considered serious.

The following hospitalizations are not considered SAEs in BHV clinical studies (but may be considered non-serious AEs):

1. A visit to the emergency room or other hospital department <24 hours that does not result in an admission (unless considered "important medical event" or event that is life threatening);
2. Elective surgery, planned prior to signing consent;
3. Admissions as per protocol for a planned medical/surgical procedure;
4. Routine health assessment requiring admission (i.e., routine colonoscopy);
5. Admission encountered for another life circumstance that carries no bearing on health and requires no medical intervention (i.e., lack of housing, care-giver respite, family circumstances).

Disability/incapacitating: An AE is incapacitating or disabling if the experience results in a substantial and/or permanent disruption of the subject's ability to carry out normal life functions.

8.1.2 Collection and Reporting Serious Adverse Events

Following the subject's written consent to participate in the study, all SAEs, whether related or not related to study drug, must be collected, including those thought to be associated with protocol-specific procedures. All SAEs must be collected that occur during the screening period and throughout the course of the study up to and including the End of Treatment Visit. The investigator should report any SAE occurring after these time periods that is believed to be related to study drug or protocol-specific procedures.

All SAEs should be followed to resolution or stabilization.

An SAE report should be completed for any event where doubt exists regarding its status of seriousness.

If the investigator believes that an SAE is not related to the study drug, but is potentially related to the conditions of the study (such as a withdrawal of previous therapy or a

complication related to study procedure), the relationship should be specified in the narrative section of the SAE Report Form.

SAEs, whether related or not related to study drug, overdose (see section 8.1.3), potential drug induced liver injury (see section 8.1.5) and pregnancies (see section 8.1.4) must be reported within 24 hours of the Investigator becoming aware of the event. For this study we will be capturing SAEs through electronic data capture (EDC) and on the SAE form.

The Investigator is responsible for reporting all SAEs and all Other Important Medical Events to CCI within 24 hours of learning of the event. CCI will then immediately notify the Biohaven Medical Monitor of the event. The Investigator is responsible for submitting all applicable events to the Independent Review Board (IRB) as per the IRB's reporting requirements. Additionally, the Investigator, or designated staff, is responsible for entering the SAE information in the Electronic Data Capture (EDC) system (i.e.: event term, start stop dates, causality, severity).

Any serious adverse event must be reported immediately or no later than 24 hours after awareness of the event to CCI Pharmacovigilance (PVG). A written description of any serious adverse event, using the CCI SAE report form, must be sent to CCI PVG by facsimile (fax) within 24 hours after awareness of the event:

- North America - 1-888-CCI

If a form is unable to be submitted within 24 hours, the SAE may be reported by telephone via the Safety Hotline Number:

- North America – 1-800-CCI

If only limited information is initially available, follow-up reports are required. If an ongoing SAE changes in its intensity or relationship to study drug or if new information becomes available, a follow-up SAE report should be sent within 24 hours of the Investigator becoming aware of the updated information using the same procedure used for the transmission of the initial SAE and the same event term should be used.

The minimum information required for an initial SAE report is:

Sender of report (Site number, Investigator name)

Subject identification (subject number)

Protocol number

SAE term (if an SAE is being reported)

8.1.3 Overdose

An overdose is defined as the accidental or intentional administration of any dose of the product that is considered excessive and medically important as determined by the investigator. All occurrences of overdose (suspected or confirmed and irrespective of whether or not it involved rimegepant or placebo) must be communicated to Biohaven or a specified designee within 24 hours and be fully documented as an SAE. Details of any signs or symptoms and their management should be recorded including details of any antidote(s) administered.

8.1.4 Pregnancy

If following the baseline visit, it is subsequently discovered that a study subject, or the female partner of a male study subject, is pregnant or may have been pregnant at the time of the investigational product exposure, including during at least 6 half-lives after the product administration, the investigational product will be permanently discontinued in an appropriate manner (i.e., dose tapering if necessary for subject's safety). Protocol-required procedures for the study discontinued and the follow-up must be performed on the subject unless contraindicated by the pregnancy (i.e., x-ray studies). Other appropriate pregnancy follow-up procedures should be considered if indicated.

Sites should instruct subjects to contact the Investigator immediately if they become pregnant during the course of the study. The Investigator must immediately notify the Biohaven Medical Monitor (or designee) of the event and complete and forward the Pregnancy Report Form to **CCI** immediately via telephone within 24 hours and in accordance with SAE reporting procedures as described in Section 8.1.2.

Follow-up information regarding the course of the pregnancy, including perinatal and neonatal outcome and, where applicable offspring information must be reported on a Pregnancy Report Form.

Any pregnancy that occurs in a female partner of a male study subject should be reported to the sponsor. Information on this pregnancy will be collected on the Pregnancy Report Form, as appropriate.

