| Assessment of Migraine Symptoms (photophobia, phonophobia, and nausea - eDiary) ¹³ | | | X | X | X | X | X | |
| Functional Disability Scale ¹³ | | | X | X | X | X | X | |
| MQoLQ (Migraine Specified Quality of Life Questionnaire) ¹³ | | | | | | X | | |
| Preference of Medication ¹³ | | | | | | X | | |

¹ **Screening Phase** will be 3 - 28 days. The **Baseline Visit** may be scheduled but should only occur *after* all screening procedures are complete, subject meets inclusion/exclusion criteria, and lab test results have been received by the site.

² Subjects will use eDiary to answer questions about their migraine symptoms upon experiencing a moderate/severe migraine headache. The subject will administer pre-dispensed study drug if 1) the headache remains moderate or severe; 2) the subject has completed all required migraine assessment questions in the eDiary, including their current most bothersome migraine symptom, and 3) the subject has not already taken prohibited medications (see protocol section 5.4).

³ Subjects should keep track of their concomitant medications throughout the study and report them to the study personnel at the End of Treatment Visit. Any medication taken for recurrent headache should be documented. Use of concomitant medications after randomization, including rescue medications, will be recorded by the subject on a paper diary and reported to the site.

⁴ Height will only be captured at the Screening Visit. Weight, body temperature, respiratory rate, blood pressure and heart rate will be collected at all time points where indicated. Sitting arterial systolic and diastolic blood pressure and pulse rate will be measured.

⁵ **Screening Visit:** All screening visit laboratory test results must be received prior to Baseline (randomization) Visit.

⁶ A serum pregnancy test will be completed at Screening and End of Treatment Visits as part of the standard laboratory tests (if appropriate). Confirmatory urine pregnancy test for WOCBP should be completed on site at Baseline Visit and any subsequent visits for confirmation at the Investigator's discretion. Home pregnancy test will be provided to WOCBP after completion of baseline visit. WOCBP subjects must complete the urine pregnancy test at home prior to taking study medication.

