⁷ SAEs are reported from the time of informed consent and non-serious AEs are reported from baseline. All ongoing non-serious AEs and SAEs will be followed to resolution or until investigator deems there will be no further status change. SAEs that occur during the treatment period should be reported to site in real time. Non-serious AEs that occur during the treatment period should be reported to the site at the EOT.

⁸ This scale will be clinician administered, completed on site, and will be in paper. The source document will be provided by Biohaven. The assessment period for completing the scale will be 30 days prior to Screening, and since the last visit for the remainder of the study.

⁹ Subjects will be randomized in the IWRS system at the Baseline Visit (Randomization Day 01).

¹⁰ Subjects should be instructed that the dose should be taken once the migraine attack reaches moderate or severe pain and after the subject has completed all required migraine assessments in the eDiary. The eDiary will prompt the subject to take study medication.

¹¹ Site staff to review and confirm entries with subjects and confirm all data points are transferred to the system and reset eDiary for future subject use, PRIOR to the subject leaving the clinic.

¹² ± Windows for timeframe around efficacy assessments (15, 30, 45, 60, 90 min, 2, 3, 4, 6, 8, 24 and 48 hours) will be automated and captured in the eDiary.

¹³ These scales will be captured in the eDiary. Subjects will also be asked about their most bothersome symptom at the time of reporting and treating a qualifying migraine.

¹⁴ Paper source document will be used to capture Migraine History. Subjects will also be asked about their typical most bothersome symptom when having a migraine.

¹⁵ Subjects should return to the site for their EOT visit within 7 (+2) days from their migraine occurring.

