 - i) Detectable levels of cocaine, amphetamine, and phencyclidine (PCP) in the drug screen are exclusionary. Subjects who are positive for amphetamines, and who are on a prescribed amphetamine medication for an approved indication (e.g. ADHD) will be allowed into the study at the Investigator's discretion. This determination by the Investigator must be well documented in the subject's source medical records. The stimulant dose must be stable from 3 months prior to baseline until the end of treatment visit occurs.
 - ii) Detectable levels of marijuana in the drug screen are not exclusionary, if in the investigator's documented opinion the subject does not meet DSM-V criteria [15] for substance use disorder, and the positive test does not signal a clinical condition that would impact the safety of the subject or interpretation of the study results.
- i) Hematologic or solid malignancy diagnosis within 5 years prior to screening. Subjects with a history of localized basal cell or squamous cell skin cancer are

eligible for the study if they are cancer-free prior to the screening visit in this study.

3. Allergies and Adverse Drug Reactions

- a) History of drug or other allergy which, in the opinion of the principal investigator, makes the subject unsuitable for participation in the study.

4. Sex and Reproductive Status

- a) Females of child-bearing potential who are unwilling or unable to use an acceptable contraceptive method or abstinence to avoid pregnancy for the entire study period and for 56 days after the study.
- b) Women who are pregnant or breastfeeding. Women with a positive pregnancy test on enrollment or prior to study drug administration.

5. ECG and Laboratory Test Findings

- a) Estimated glomerular filtration rate (eGFR) according to the re-expressed abbreviated (four-variable) Modification of Diet in Renal Disease (MDRD) Study equation $\leq 40 \text{ ml/min/1.73m}^2$
- b) Corrected QT interval $> 470 \text{ msec}$ (QTc by method of Frederica), at Screening
- c) Left Bundle Branch block
- d) Right Bundle Branch Block with a QRS duration $\geq 150 \text{ msec}$.
- e) Intraventricular Conduction Defect with a QRS duration $\geq 150 \text{ msec}$.
- f) Serum bilirubin (Total, Direct or Indirect) $> 1 \text{ x ULN}$ (Only abnormal values of between 1-1.5x ULN may be repeated once for confirmation during the screening period)
- g) Neutrophil count $\leq 1000/\mu\text{L}$ (or equivalent).

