5.5 Women of Childbearing Potential

Women of childbearing potential (WOCBP) include any female who has experienced menarche and who has not undergone successful surgical sterilization (hysterectomy, bilateral tubal ligation, or bilateral oophorectomy) or is not postmenopausal. Post menopause is defined as:

1. Amenorrhea greater than or equal to 12 consecutive months without another cause and a documented serum follicle stimulating hormone (FSH) level $> 35\text{mIU/mL}$ or
2. Woman with irregular menstrual periods and a documented serum follicle stimulating hormone (FSH) level $> 35\text{mIU/mL}$ or

NOTE: FSH level testing is not required for women greater than or equal to 62 years old with amenorrhea of greater than or equal to one year

3. Woman on hormone replacement therapy (HRT)

Women of childbearing potential (WOCBP) with male partners and men with women partners of childbearing potential must be using two acceptable methods of contraception to avoid pregnancy throughout the study and for up to 56 days after the last dose of investigational product in such a manner that risk of pregnancy is minimized. It is required that all WOCBP use two methods of contraception for the duration of the study (i.e. beginning before treatment with the 1 dose of study medication to 56 days after dosing). The two methods should include one barrier method (i.e. condom with spermicidal gel, intrauterine devices, cervical cap etc.) and one other method. The other method could include oral contraceptives or another barrier method (note, an Intra Uterine Device is considered one method).

Women who suspect that they have become or may have become pregnant despite using proper birth control methods, should use the home pregnancy test provided at Baseline Visit. Home pregnancy test should be administered prior to taking Investigational Study Drug. Subjects should not take Investigational Study Drug if they are pregnant and subject should immediately contact Study Investigator.

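### The protocol's pregnancy windows disagree, and for 47 to 49 of the 56 post-dose contraception days there is no scheduled test and no clear instruction to report a pregnancy

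*Protocol*

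**What the plan says.** **Contraception.** Protocol 5.5 requires two methods "throughout the study and for up to 56 days after the last dose of investigational product". The next sentence restates this for the length of the study, explained in a parenthesis: "i.e. beginning before treatment with the 1 dose of study medication to 56 days after dosing". Exclusion 4a in 5.3 counts from a different point: "for the entire study period and for 56 days after the study".

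**Exposure.** Section 8.1.4 covers a subject, or a male subject's partner, later found to be pregnant or possibly pregnant at exposure, "including during at least 6 half-lives after the product administration". No half-life value is visible in the protocol text.

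**Testing.** Under Table 1, footnote 6, "A serum pregnancy test will be completed at Screening and End of Treatment Visits". Women of childbearing potential also have a urine test at Baseline and a home test before dosing. On the timing of the last visit, footnote 15 says: "Subjects should return to the site for their EOT visit within 7 (+2) days from their migraine occurring". Section 4.3.4 gives the same 7 (+2) days, counted from treatment. No later visit, call or test is described.

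**Reporting.** Section 8.1.4 says: "Sites should instruct subjects to contact the Investigator immediately if they become pregnant during the course of the study". It also requires follow-up of pregnancy, perinatal and neonatal outcomes, and reporting of partner pregnancies with no stated time limit. Section 8.1.2 has the investigator report any pregnancy within 24 hours of learning of it. That section also uses the same phrase about the course of the study for collecting serious adverse events, and ends it explicitly at the End of Treatment Visit.

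**The concern.** Three windows (56 days from the dose, 56 days from the end of the study, six half-lives) govern one subject matter, and the subject's own instruction follows none of them. A site cannot tell from the text whether a woman who conceives on day 30 after the dose should have been told to call.

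The protocol asks women to avoid conceiving for weeks after the dose and requires pregnancy outcomes to be followed. If the request to report lapses at the last visit, a low or zero count of pregnancies says little about most of the contraception period, because nobody asked during it. The matter is one of safety ascertainment only.

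**Working it through.** All days are counted from the dose. (The SAP's Study Day 1 is randomization, so these are not study days.)

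**1. Where does the study end?** Section 4.1 states a total of about 11 weeks. Its components are screening of up to 28 days, an acute phase of up to 45 days and a final visit 7 days after dosing.
- Ending at the final visit: 28 + 45 + 7 = 80 days; 80 / 7 = 11.4 weeks. With the +2-day allowance: 82 / 7 = 11.7 weeks.
- Ending 56 days after the dose: 28 + 45 + 56 = 129 days; 129 / 7 = 18.4 weeks.

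The stated duration is reproduced only if the study ends at the End of Treatment Visit. Section 8.1.2 agrees. So do the first contraception sentence of 5.5 and exclusion 4a, both of which name the study and the 56 days as separate periods. The parenthesis in 5.5 points the other way.

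**2. Share of the contraception period after the last test and the instruction.** Formula: (56 − day of last visit) / 56.
- Visit on day 7: 49 / 56 = 87.5%.
- Visit on day 9: 47 / 56 = 83.9%.

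An earlier visit leaves a larger share.

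**3. With exclusion 4a's anchor.** The 56 days start when the study ends, so all 56 fall after the last test. Counted from the dose, the period runs 7 + 56 = 63 to 9 + 56 = 65 days, and the part after the last visit is 56 / 63 = 88.9% or 56 / 65 = 86.2%.

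**4. Can the half-life window be compared?** Not from these documents. Six half-lives fit inside 7 days if the half-life is at most 7 × 24 / 6 = 28 hours, and inside 9 days if it is at most 9 × 24 / 6 = 36 hours. They equal 56 days only at 56 × 24 / 6 = 224 hours. With no half-life shown, and a window stated as a minimum, its end cannot be placed on the calendar.

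**The case against.** The best reply is that a contraception period is not an exposure period. Section 5.5 sets a precaution and may deliberately run longer than the time the drug is present. The only exposure window is the one in 8.1.4, and by step 4 it may close before the last visit. This stands. A reader might infer that the protocol regards all 56 days as exposed and leaves exposed pregnancies unobserved; the documents do not say that, and 84 to 88% is a share of contraception days only.

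Second, pregnancies can still come to light. The clause in 8.1.4 on later discovery has no calendar end, partner pregnancies have no stated limit, and the investigator must report whatever he or she learns. This also stands, and rules out saying that such pregnancies would be lost. But each route needs the investigator to find out, and the one instruction that would bring a subject's own pregnancy forward is tied to the study.

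Third, the parenthesis in 5.5 could stretch the reporting duty to 56 days. That is possible, though the stated duration and 8.1.2 weigh against it. Even then no test or contact is scheduled after the last visit, and sites still face conflicting text.

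Fourth, the consent form is not among the documents available here, and the pregnancy surveillance forms listed in 6.1 are not reproduced. Either might carry a later instruction. The finding is therefore about the protocol text.

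Two further inferences should be resisted. The documents give no test sensitivity, so nothing can be said about which conceptions the last serum test would miss. Nor do they give the number of treated women of childbearing potential or a pregnancy rate. Assuming 250 to 400 women per arm and 1 to 6% per woman-year, pregnancies beginning after the last visit would range from 250 × 0.01 × 47 / 365 = 0.3 to 400 × 0.06 × 49 / 365 = 3.2 per arm. Those inputs are assumptions, the two-method requirement makes the upper end hard to defend, and the finding does not depend on them.

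**Conclusion.** The inconsistency is real: three windows with different anchors or units, and a reporting instruction aligned with none of them. On the better-supported reading, that the study ends at the End of Treatment Visit, 84 to 88% of the post-dose contraception days rely on passive reporting. This rests on the visit falling on day 7 to 9 and on reading the course of the study in 8.1.4 as 8.1.2 does. On the wider reading, the subject's duty to report covers the 56 days, but scheduled testing still stops at the last visit.

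Whether any of the protocol's own exposure window goes without scheduled observation cannot be determined from the documents. The point is worth correcting because the wording is ambiguous on a safety matter and the repair is cheap. It has no bearing on the efficacy analysis, the error rate or the sample size.

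**What to change.** Reconcile exclusion 4a (5.3), 5.5, 8.1.2 and 8.1.4 so that one sponsor-chosen window, with one anchor, governs both the contraception requirement and the subject's instruction to report a pregnancy. Have sites give that instruction at the End of Treatment Visit, with reports going on the existing Pregnancy Report Form. State how the six-half-life window relates to the chosen one. That phrase also governs discontinuation of the product, so its content is for the sponsor to settle; no duration or treatment-stopping rule is proposed here. Check that the consent form says the same.

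The cost is a wording change, with the ethics approval that Section 11 requires for an amendment, and one instruction at an existing visit. No new visit, test or form is needed. The small downside is that a few reports may arrive after database lock and would be held in the safety database.
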